1.0 Objectives

1.1 Study Objectives

Our central hypothesis is that Cannabidiol will result in a significant improvement of endometriosisrelated pain. This proposal seeks to (1) determine if cannabidiol will result in an overall improvement of patient-reported endometriosis associated pain (2) determine if this pain reduction is dose-dependent (3) determine if cannabidiol will result in improved sexual function (4) determine if cannabidiol will result in an overall improved quality of life among women with endometriosis (5) determine if CBD affects common inflammatory markers associated with endometriosis (6) to determine the pharmacokinetics of sublingual CBD. We propose a randomized double-blind placebo-controlled pilot study to achieve the following aims:

Aim 1: Identify the overall impact of cannabidiol (CBD) on endometriosis related pain. We plan to measure endometriosis related pain using daily self-reported Visual Analogue Scale (VAS) scores over an 8 week period.

Aim 2: Identify the dose-dependent impact of cannabidiol on endometriosis related pain. We will be dividing our patients into 3 arms – high dose CBD, low dose CBD and placebo. We plan to measure and compare endometriosis related pain using daily self-reported Visual Analogue Scale (VAS) scores.

Aim 3: Identify the overall impact of cannabidiol (CBD) on sexual function. This will be assessed via the Female Sexual Function Index (FSFI), a validated survey, to be administered to participants with current sexual partners that are sexually active.

Aim 4: Identify the impact of cannabidiol on Quality of Life (QOL) among women with endometriosis. We plan to measure QOL using the Endometriosis Health Profile-30 (EHP30), Patient Global Assessments (PGAs), and Patient Global Impression of Change (PGIC) surveys. These are validated health surveys.

Aim 5: To measure inflammatory cytokines that have been linked to the pathogenesis of endometriosis and to determine if CBD will alter these inflammatory markers.

Aim 6: On a small subset of patients (4), we will study the pharmacokinetics of sublingual CBD.

1.2 Primary Study Endpoints

The primary study endpoint is the difference in endometriosis associated pain as reported in daily VAS between study groups.

1.3 Secondary Study Endpoints

- (1) To determine the difference in QOL measurements between study groups. The EHP30 is a validated survey used to measure quality of life outcomes in women with endometriosis. PGIC and PGAs are routinely used in endometriosis clinical trials to assess outcome measures such as dysmenorrhea, non-menstrual pelvic pain and dyspareunia.
- (2) To identify the overall impact of CBD on sexual function among participants that are currently partnered and sexually active.
- (3) To measure inflammatory cytokines and determine their levels before, during and at the end of the treatment cycle.
- (4) To determine the pharmacokinetics of sublingual CBD

We will record pain medication usage (opioid and non-opioid). Subject reported side effects will also be monitored.

2.0 Background

2.1 Scientific Background and Gaps

Endometriosis is a clinical disease defined by the presence of endometrial glands or stroma outside of the uterine cavity. Primary symptoms include chronic pelvic pain, dysmenorrhea, dyspareunia, and infertility. It is estimated to effect up to 10% of the general female population and accounts for a disproportionately large number of women with chronic pelvic pain.¹⁻² Endometriosis can have a profound impact on not only a woman's physical health, but also on their social and mental well-being.

Multiple theories exist as to the pathogenesis of endometriosis. The most commonly described is that of Sampson's Theory. According to this theory, the endometrial lining within the uterus sheds during menstruation and refluxes backwards through the fallopian tubes into the abdominal cavity. This efflux primarily settles and implants itself into the dependent portions of this space, which explains the disease's most common locations, i.e. the ovary, rectovaginal space, bladder surface and pelvic sidewalls. We also suspect that there are genetic and environmental factors that predispose specific women to become affected. On the other hand, endometriosis in extra-pelvic and extra-abdominal locations lends strength to alternative theories such as coelomic metaplasia and stem cell dysfunction.¹

There are many challenges in the diagnosis and treatment of endometriosis. Endometriosis is poorly visualized on current imaging modalities and is unable to be diagnosed via any known laboratory values. Current standards require surgical intervention with biopsies confirming suspected histopathology. Given the invasive nature of this route and the variability of the disease's course, it is common for women to have a lengthy delay in their diagnosis, ranging on average from 7 to 11 years. ¹⁻²

Currently, there is no cure for endometriosis. Even after complete surgical sterilization, endometriosis and endometriosis related symptoms can persist.³ Standard of care involves a combination of lifestyle modification, hormonal and nonhormonal medications and surgical intervention with thought given to the patient's fertility desires. Traditional physician directed medical therapies include a combination of anti-inflammatories and hormones. ⁴ Unfortunately, many women also will eventually incorporate opioid pain medication into their treatment plan. Women with endometriosis have a higher probability of prolonged use and/or concomitant use with benzodiazepines than the general population.⁵ Due to the well-recognized opioid epidemic, there is a need to explore alternative treatments for pain, particularly if patient's are already seeking out these drugs for personal use in uncontrolled settings.

Cannabis is a well-known plant that contains more than 500 identified phytochemicals, of which over 100 are cannabinoids. The most widely studied is Δ^9 -tetrahydrocannabinol (Δ^9 -THC), which is the major psychoactive component of *Cannabis*, but Cannabidiol (CBD) has been increasingly favored for its reduced side effect profile and potential health benefits. CBD was first isolated from *Cannabis* in the 1940s. Both CBD and Δ^9 -THC have been shown to have profound effects on human physiology through primarily what is known as the endocannabinoid system (ECS).⁶

The ECS is a group of endogenous receptors, ligands, enzymes and proteins, which are located predominantly in both the central and peripheral nervous system. The ECS has been shown to have direct effects on motor function, eating habits and of more specific interest to us, it has been shown to affect mood, immunocompetency, cell proliferation and inflammation.⁷⁻⁸ Endocannabinoids are lipid derived ligands that bind to cannabinoid, vanilloid and peroxisome proliferator-activated receptors (PPAR).⁶

The mechanism of pain in endometriosis is complex and not entirely understood. It can be loosely divided into 3 types of pain (1) Nociceptive Pain (2) Inflammatory Pain (3) Neuropathic Pain. Nociceptive pain occurs in the peripheral nervous system (PNS) as a transfer of noxious stimuli via superficial or visceral receptors. Endometriosis lesions can cause mechanical pain via compression and infiltration.¹¹

Endometriosis is also regarded as a chronic inflammatory state; peritoneal fluid in these patients is notable for an upregulation of nerve growth factor secondary to increased levels of inflammatory cytokines, TNF-alpha, interleukin-1beta and highly oxidated byproducts.⁸ Finally, neuropathic pain results from damage to neurons and processes such as central sensitization of pain. Changes in gray matter have been shown in patients with endometriosis and chronic pelvic pain versus healthy controls.⁹

 Δ^9 -THC exerts its effects via the ECS by mimicking endogenous cannabinoids and binding primarily to the aptly named cannabinoid type 1 (CB1) and cannabinoid type 2 (CB2) receptors.⁸ Both are G-protein coupled receptors of which the former is found primarily in the brain and several peripheral tissues, such as the uterus, while the latter is seen affecting immunologic and gut cell function.⁸

While CBD does demonstrate a low affinity for CB2 receptors, it acts primarily through alternative mechanisms both within and outside of the ECS system depending on its dose¹⁰. At low concentrations, it can (1) enhance the activity of the serotonin 5-HT_{1a} receptor (2) enhance activity at glycine receptor subtypes (3) effect the transient receptor potential of ankyrin type 1 (TRPA1) channel (4) inhibit orphan G-protein coupled receptor GPR55.^{6,9} Activity at the serotonin receptor may have positive effects on mood, while glycine receptors have been associated in analgesia and pain modulation. Activity at the TRPA1 channel may explain its effect in reduction in neuro-excitability and seizure threshold. Finally, although not well understood, GPR55 has been identified in the ECS pathway. Together, these may have positive effects on primarily nociceptive and neuropathic pain.

At higher levels, CBD has also been shown to activate the (PPAR- γ) and vanilloid receptors. ⁶ Many of the studies on the ECS and endometriosis related pain have focused on *Npalmitoylethanolamine* (PEA), which is a minor constituent of the endocannabinoid ligand, *N*arachidonollethanolamine (AEA). PEA activates the PPAR receptor pathway and enhances the ECS. Studies have demonstrated that the addition of PEA significantly improves pelvic pain, reduces dyspareunia and improves sexual function.⁸ On the other hand, CBD has been shown to activate vanilloid receptors; these receptors have been found to be upregulated in the peritoneal fluid of endometriosis patients as well in patients with deeply infiltrative endometriosis. ¹¹⁻¹²

Finally, aside from alteration of pain and pain's perception in endometriosis patients, the cannabinoid system has been shown to be involved in numerous other pathways that may serve to alter the course of the disease. Cannabinoids have been implicated in the modification of cellular apoptosis, cellular migration (e.g. in cases of deeply infiltrative endometriosis), inflammation, and angiogenesis; therefore, there may be benefits of the drug to potentially modify the course of endometriosis.¹³

In summary, endometriosis is a chronic, debilitating disease that affects up to 10% of reproductive age women. Its pathophysiology is not entirely understood, but there is good evidence that inflammation and abnormal cell proliferation play a role. Current strategies for management of endometriosis pain and related symptoms often leave women unsatisfied or seeking additional treatment in the form of opioids and alternative therapies. Recent legislation (Agricultural Act of 2018) has made CBD products widely available to the average consumer. This bill descheduled hemp (any *Cannabis* variety containing less than 0.3% THC content) from the definition of marijuana in the Controlled Substances Act. Moreover, it loosened regulations on its sale and distribution. Given increasing patient interest and access to a variety of poorly monitored CBD products, it is important to study its potential therapeutic benefit in a controlled manner.

2.2 Previous Data

We do not have any preliminary data specific to the use of cannabidiol in the treatment of endometriosis related pain symptoms. The results of this study would potentially serve as preliminary data for future large multi-center studies.

There is sufficient preliminary data (for alternative disease states) in the existing literature regarding the safety and potential efficacy of Cannabidiol to support the further study of this drug.

Data has been published on the safety and efficacy of CBD in the treatment of epilepsy. Recently, a multicenter interventional trial was conducted by Devinsky, et al. to examine whether the addition of CBD would decrease seizure rates among patients with severe, refractory childhood-onset epilepsy. Their findings suggested a significant reduction in monthly motor seizures with an acceptable safety profile. ¹⁴ In June 2018, the U.S. Food and Drug Administration (FDA) approved the orphan drug, Epidiolex (Cannabidiol), which is an oral solution, to be used for two rare forms of severe epilepsy, Lennox-Gastaut syndrome and Dravet syndrome.

To date, several *Cannabis* related drugs have been approved for varying indications. Nabilone, a CB1/2 receptor agonist was approved for chemotherapy related nausea in 1981. Marinol (Δ^9 -THC) was approved in 1985 as an anti-emetic and for excessive weight loss in patients with acquired immune deficiency syndrome (AIDS). In 2005, Sativex, a *Cannabis* derivative, was also approved for the treatment of cancer-related pain and neuropathic pain associated with multiple sclerosis.¹³

2.3 Study Rationale

Endometriosis is a chronic pelvic pain condition that affects up to 10% of female reproductive age women. Endometriosis has no cure and is associated with a decreased quality of life. At some point in their disease course, not only will many women will turn to opioids for pain management, they are more likely to seek off-label poorly studied therapies. Therefore, there is a need for more data on non-opioid management options for these patients obtained in a safe and controlled manner.

CBD is a phytocannabinoid derived from the Cannabis plant. Since the Farm Bill of 2018, it has been become widely popularized and distributed to the general population. CBD is known for less psychotropic effects than its counterpart, Δ^9 -THC, but with potentially similar effects on pain perception, inflammation, cell-growth and regulation. Although the pathophysiology of endometriosis is not entirely understood, there is good evidence that inflammation and abnormal cell proliferation play a large role. We believe that CBD will result in a reduction in endometriosis associated pain.

We also carefully considered the following (1) CBD manufacturer (2) appropriate dosing for our intended indication and (3) ease and route of patient administration.

- (1) In regards to the first issue, there are currently no federal or state regulated CBD dispensaries. Therefore, in order to obtain a quality study drug, we initially chose 3 reputable online companies and performed independent validity testing of the potential sublingual CBD sources at Penn State Health. We have worked closely in conjunction with [name], the Chair of Pharmacology, and his laboratory in order to test the intended study drugs and to develop the protocol. From our initial round of testing, we chose the product with the most accurate CBD content (Nuleaf Naturals). During the FDA IND application process, we performed a second round of testing on the intended study drug to ensure safety up to FDA guidelines, which included microbial and mycotoxin testing.
- (2) In the literature, there is a wide variety of CBD dosages cited ranging as high as 800mg oral daily. From what is known about the pharmacokinetics of CBD, it undergoes extensive first pass metabolism and absorption via oral route is only roughly 6%. Therefore, we chose a sublingual route to increase bioavailability.¹⁰ Furthermore, high oral dosages have been reported in a variety of studies, but they have primarily been examining neurologic conditions such as epilepsy,

schizophrenia, and Parkinson's disease. Although few published trials have used a sublingual mode of delivery for CBD, it is actively being studied in multiple ongoing clinical trials.

A search conducted on 7/2/20 on clinicaltrials.gov yielded 81 registered trials looking specifically on CBD and pain. We identified studies involving a sublingual mode of delivery of which the results are summarized below. As demonstrated in the table, most dosing for sublingual CBD ranges from 5-20mg per dose.

TRIAL NUMBER	DOSE	INDICATION
NCT 03948565	20mg BID sublingual oil	Chronic Pain
NCT 04271917	8.5 mg as needed	Dental Pain
	18.5mg as needed sublingual oil	
NCT 04298554	20mg qD sublingual	TMJ Pain
NCT 04195269	10mg CBD/10mg THC BID sublingual	Osteoarthritis Pain
	tablet	
NCT 04088929	20 mg TID sublingual tablet	Diabetic Neuropathy
NCT 04193631	5mg as needed sublingual tablet	Musculoskeletal pain
15 Different Trials	Sativex	Various Pain
	2.5mg THC/2.5mg CBD per spray	
	Up to 8 sprays/3 hours (20 mg) or 48	
	sprays/24 hours (120mg) Buccal Spray	

Per the recommendations form our Co-Investigators from Pharmacology, it was also decided that given the long half-life of CBD, multiple doses per day for chronic users would not likely substantially affect the concentration of CBD. Therefore, we believe that sublingual administration of 10 to 20mg daily will be adequate to achieve an effect for our intended indication.

(3) In regards to patient administration of the study drug, we conducted a small focus group in order to determine the best way to administer the sublingual doses of the study drug. We considered the administration of 8 total drops of CBD at once, held under the tongue for one minute then swallowed, versus 4 drops held under the tongue for one minute then swallowed followed by an additional 4 drops. We concluded that 8 drops were a difficult volume to tolerate for the average study participant. If we were to increase the dose, we believe it would start to affect tolerability.

3.0 Inclusion & Exclusion Criteria

3.1 Inclusion Criteria

1. Females ages 18-45 years at the time of enrollment

2. A surgical diagnosis with direct visualization and/or histopathologic confirmation of endometriosis with associated moderate to severe endometriosis related pain (> 3 on a VAS)

3. Is not expected to undergo gynecological surgery or other surgical procedure for treatment of endometriosis during the study period

4. Agrees to use approved contraception method during the entire study

5. Patients using oral contraceptives, vaginal ring, injectable progesterone and/or GnRH agonists/antagonist for contraception and/or management of endometriosis, can be included if both they and their primary provider agree to stopping their medication and transitioning to Norethindrone acetate (NETA) as the primary treatment of endometriosis throughout the study period.

6. Patients using a progesterone containing IUD or a copper IUD for contraception and/or management of endometriosis can be included if both they and their primary provider agree to initiate Norethindrone (NETA) as the primary treatment of endometriosis throughout the study period

3.2 Exclusion Criteria

- 1. Women that are pregnant, breastfeeding or trying to conceive
- 2. Women with chronic daily opioid use and any chronic pain or frequently reoccurring pain condition, other than endometriosis, that is treated with opioids for \geq 10 days per month.
- 3. Women who have had a bilateral oophorectomy
- 4. Women that are currently using *Cannabis* based products and are unwilling to stop for 30 days prior to study enrollment and for the study duration
- 5. Non-English speaking or inability to read and understand English
- 6. Women with a BMI > 35 kg/m^2
- 7. Women with known liver disease, such as hepatitis, or with screening LFTS (AST/ALT) > 3 times above the upper limits of normal (ULN) in the past year
- 8. Women with chronic alcohol use (defined as \geq 3 drinks per day, averaged over one week)
- 9. Women with chronic use of drugs (defined as ≥ 10 days/month) that cause somnolence/sedation such as benzodiazepines or Central Nervous System (CNS) depressants that are unwilling or unable to discontinue the medications for the washout period and the duration of the study
- 10. Women who are currently taking Clobazam or Valproate and are unwilling/unable to discontinue the medication for the washout period and the duration of the study
- 11. Women with suicidal ideation or uncontrolled depression within the past year
- 12. Known history of or suspected breast cancer on screening physical exam
- 13. History of or active deep venous thrombosis or pulmonary embolism
- 14. History of or active arterial thromboembolic event (e.g. stroke, myocardial infarction)
- 15. Multiple (> 3) risk factors for arterial vascular disease (e.g. uncontrolled hypertension, diabetes mellitus, hypercholesterolemia, obesity and smoking)
- 16. Current use of a progestin-containing contraceptive implant

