7.2.1 Prescreen

Patients will be screened and recruited as outlined in Section 4, Recruitment Methods. If they meet outlined criteria they will be contacted by the study coordinator for Study visit 1 - Screening Visit.

During prescreening, the subject will confirm whether she is currently taking hormonal medication for contraception and/or endometriosis related issues. Depending on her current medication, she may need to delay enrollment into the study. If they are not already on NETA, they will need to consult with their primary physician in order to initiate the medication. Patients will also be advised to consult with their primary physician in order to determine whether they can initiate NETA and stop their current medication regiment. Once the patient is enrolled in the study, NETA will be provided by the IDS.

If the patient is not currently on NETA, they will need to be transitioned as follows:

- 1. None No delay
- 2. Combined oral contraceptive No delay
- 3. Etonogestrel/ethinyl estradiol vaginal ring No delay
- 4. GnRH antagonist (e.g. Orlissa) No delay
- 5. Long acting reversible contraception (Progesterone IUD, Copper IUD) No delay
- 6. GnRH agonist (e.g. Lupron Depot): 3.75 mg must wait 1 month from administration of prior injection and 11.25 mg- must wait 3 months from administration of prior injection.
- 7. Injectable Progesterone (Depo Provera) Must wait 3 months from administration of prior injection
- 8. Progestin-containing contraceptive implant Excluded from the studied

For women using methods listed #1-4, they will stop/remove this form of contraception and be transitioned immediately to NETA.

For women using LARCS listed #5, they can continue this form of contraception and be transitioned immediately to NETA.

For women using methods #6-7, they must wait the listed time prior to initiation of NETA.

All subjects will be required to be on NETA for 30 days prior to the enrollment visit.

The NETA is intended for the purposes of endometriosis related standard of care and is not considered an appropriate contraceptive method for patients. Acceptable methods of contraception are listed in Section 7.2.3.

We will confirm they are not currently taking any of the exclusionary medications/drugs in their described manners. If they have recently stopped the below products, their required washout period is listed below:

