- 1. *Cannabis* based products (this will be further confirmed on toxicology testing at the screening visit) (required washout period: 30 days)
- Chronic daily use of drugs (≥ 10 days/month) that cause somnolence/sedation such as benzodiazepines or Central Nervous System (CNS) depressants (required washout: 30 days)
- 3. Clobazam (required washout period: 14 days)
- 4. Valproate (required washout period: 14 days)

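### Exclusions 9 and 10 let a woman qualify by stopping clobazam, valproate or a chronically used sedative, without requiring her prescriber's agreement or naming who judges whether she can stop

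*Combined protocol and SAP*

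**What the plan says.** Two exclusions in section 3.2 are conditional. Exclusion 10 covers women "currently taking Clobazam or Valproate and are unwilling/unable to discontinue the medication for the washout period and the duration of the study". Exclusion 9 covers women who use sedating drugs on at least 10 days a month, such as "benzodiazepines or Central Nervous System (CNS) depressants that are unwilling or unable to discontinue the medications for the washout period" and for the study.

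Section 7.2.1 puts this into practice. Staff confirm that the drugs are not being taken, and then: "If they have recently stopped the below products, their required washout period is listed below". The list gives "benzodiazepines or Central Nervous System (CNS) depressants (required washout: 30 days") and "Valproate (required washout period: 14 days"), with 14 days for clobazam as well.

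For hormonal treatment, section 3.1 goes further. Under inclusion 5, users "can be included if both they and their primary provider agree to stopping their medication and transitioning to Norethindrone acetate (NETA"). Inclusion 6 also asks for provider agreement when an IUD user starts NETA, although she keeps her IUD. Section 7.2.1 adds that patients are "advised to consult with their primary physician in order to determine whether they can initiate NETA and stop their current medication regiment".

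**The concern.** For clobazam, valproate and chronic sedatives, the eligibility rule can be met by the woman's own decision to stop. The text does not ask that the clinician who prescribed the drug agree to the stop or direct it. The protocol does ask for provider agreement before a hormonal treatment is stopped. So the stated condition of entry is lighter for an anti-seizure or sedative drug than for a contraceptive.

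What is at stake is the safety of a small number of women. That stopping such a drug without supervision can carry withdrawal or seizure risk is clinical judgement; the protocol gives no figure for it. No bias in the pain endpoint is claimed. Keeping these drugs away from CBD is reasonable: section 10 reports that most transaminase elevations occurred with concomitant valproate and, to a lesser degree, clobazam. The question is only how a current user comes to be off the drug.

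**Working it through.** The protocol states no figure on this point and the finding needs no arithmetic. The check sets the relevant texts side by side and asks whether any of them makes the prescriber's agreement a condition of entry.

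1. **Exclusions 9 and 10 (3.2).** The test is whether the woman is unwilling or unable to stop. A current user who is neither is not excluded. No clinician is mentioned.
2. **Inclusions 5 and 6 (3.1).** The test is joint agreement of the woman and her primary provider. Inclusion 5 covers stopping one treatment and moving to NETA; inclusion 6 covers adding NETA. The safeguard is therefore already drafted, but only for hormonal management.
3. **Advice to consult (7.2.1).** The sentence about consulting the primary physician sits in the paragraph on current hormonal medication and the move to NETA. The drugs in exclusions 9 and 10 are taken up later in that section, in a separate paragraph. The sentence is also advice and not an entry condition.
4. **Washout list (7.2.1).** It gives durations only: 14, 14 and 30 days for these drugs.
5. **Screening visit (7.2.2).** The history looks specifically for anti-epileptic use and there is a thorough medication review. Both are done by the study team, and contact with a prescriber is not mentioned.
6. **Prior and concomitant therapy (7.4.6.5).** It only points back to 7.2.1.
7. **Who screens (4.2.1 to 4.2.4).** A study coordinator assesses eligibility by a scripted telephone call. Candidates may be self-referred or come through a gynecologic surgery clinic, so the prescriber of an anti-seizure or sedative drug need not be part of the process.
8. **End of treatment (7.2.5, 7.2.6).** A woman who wishes to stay on NETA is referred to her OB/GYN. No referral is stated for a drug she stopped in order to qualify.

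None of these texts supplies the missing condition, and none says who decides that a woman is unable to stop.

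**The case against.** The strongest reply rests on the word 'unable'. Exclusion 4, on cannabis, turns only on willingness. Exclusions 9 and 10 add inability, and the natural reading of that contrast is that some women medically cannot stop these drugs. Section 7.2.2 then requires a careful medication review, and section 7.2.3 allows randomization only if all criteria are met. This stands as a reading of intent. It does not say who judges inability, or that the prescriber must be asked.

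A second reply is that provider agreement in section 3.1 attaches partly to starting NETA, a treatment the protocol requires, and not only to stopping something. Inclusion 6 bears this out, so the comparison is not exact. Inclusion 5 nevertheless names the stop as something both parties must agree to.

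A reader might infer four stronger things that the documents do not support:

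- **That staff tell women to stop, or that no prescriber would be involved.** Section 7.2.1 speaks of women who have recently stopped, and no text has staff instruct a stop. The telephone script and consent form were not available and could contain such a safeguard.
- **That the stop must begin before written consent at Visit 1.** Counting a 30-day washout back from an enrollment visit 7 to 14 days after Visit 1 would put the start 30 − 14 = 16 to 30 − 7 = 23 days before consent. But the protocol does not say from which date these washouts are counted, nor that the 1-2 week interval is fixed. It also states "All subjects will be required to be on NETA for 30 days prior to the enrollment visit", while section 7.2.2 lets NETA start at Visit 1, so enrollment can evidently fall later than two weeks. If the washout can delay enrollment in the same way, a 30-day washout can begin at Visit 1 (30 − 30 = 0 days before).
- **That the length of time off the drug measures harm.** It does not, and no such figure is used here.
- **That women who leave early are left without follow-up.** Section 3.3.2 already leaves the care of women removed under section 3.3.1 to their physician team, so no addition is needed there.

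**Conclusion.** The point holds in a limited form. Within the protocol text, a woman taking clobazam, valproate or a chronic sedative can meet the eligibility rule by stopping it. Her prescriber's agreement is not required, and no one is assigned to judge whether she is able to stop. This is more than missing detail, because supplying it adds a real condition of entry.

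It is a minor patient-safety improvement. The documents give no prevalence for these drugs; the assumption is that few of the 36 women would be affected. The conclusion also assumes that the telephone script and consent form do not already require prescriber agreement, which could not be checked. It implies nothing about the sample size, the analysis or the endpoints.

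**What to change.** In exclusions 9 and 10 and in the section 7.2.1 washout list, admit a current user only if both she and the provider who prescribes the drug agree to the discontinuation and that provider directs it. State that the provider's judgement decides whether she is unable to stop. Record the agreement before the washout starts, for example in one field on the prescreening form. In section 7.2.6, add a line referring her back to that prescriber at the end of the study about restarting. Whether these drugs should be stopped for the trial at all is a clinical decision and is left open here.

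The cost is one phrase in two criteria and in the washout list, one form field and one line at the final visit. The planned 36 participants, the visit schedule and the analysis do not change. The downside is that a few candidates may be lost if a prescriber declines, or delayed if the prescriber is slow to respond.
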